## **DOCUMENT HISTORY**

Document	Date of Issue	Summary of Change
Original Protocol	27 June 2022	Not Applicable
Version 1.1	1 September 2022	Administrative changes Addition of paragraph regarding patient recovery from surgery in section 3.4.1 Addition of biomarkers in section 3.5.2 Addition of subgroup analysis in section 4.1.1.4

Model Document Version 04-Jun-2021

### SYNOPSIS

#### **Observational Study Protocol BMS-CA209-6KX**

**Protocol Title:** Prospective Evaluation of Nivolumab in Adjuvant Esophageal Cancer/Gastroesophageal Junction Cancer: A Non-interventional Study

**Department:** WW Health Economics & Outcomes Research (WWHEOR)

#### **Objective(s):**

Primary Objective: The primary objective of this study is to estimate real-world disease-free survival (DFS) in adult patients with early-stage esophageal cancer (EC) or gastroesophageal junction cancer (GEJC) initiating adjuvant nivolumab treatment.

#### Secondary Objectives:

The following secondary objectives will be assessed overall and according to various subgroups of interest, unless otherwise specified:

- To estimate in adult patients with early-stage EC or GEJC initiating adjuvant nivolumab treatment:
  - o DFS and DFS rates in subgroups of interest
  - Median overall survival (OS) and OS rates
  - o Distant metastasis-free survival (DMFS) and DMFS rates
- To describe disease recurrence patterns in patients with a recurrence, including time to recurrence, type of recurrence (local/regional vs metastatic), and post-recurrence survival (PRS)
- To describe treatment patterns of adjuvant nivolumab (dosing, regimen, indication, treatment rationale, treatment duration, modifications in relation to the management of adverse events [AE], reasons for treatment discontinuation/cessation), subsequent therapy (regimen(s), duration), and time to next treatment (TTNT)
- To estimate from initiation of subsequent treatment, in patients that receive subsequent treatment(s) following adjuvant nivolumab discontinuation:
  - o OS and OS rates
  - Progression free survival 2 (PFS2) and PFS2 rates
  - Overall response rate (ORR)
- To describe sociodemographic and clinical characteristics, and treatment history
- To describe incidence and severity of adverse events (AEs) and serious adverse events (SAEs) in relation to nivolumab

Exploratory Objective: The exploratory objective of this study is to evaluate patient satisfaction with adjuvant nivolumab treatment using the Cancer Therapy Satisfaction Questionnaire (CTSQ) and health related quality of life (HR-QoL) by using the Functional Assessment of Cancer Therapy – General 7 item version (FACT-G7) questionnaire.

**Study Design:** This is a non-interventional, prospective, multinational, multicenter, post-marketing observational study designed to describe the effectiveness and patterns of use of adjuvant nivolumab after resection in patients with early stage (Stage II/III) EC/GEJC. This study will be conducted in the United States (US) and Germany will only collect data available from patients' medical files and other items

routinely collected during disease management in clinical practice. This study is strictly observational, and prescriptions of nivolumab will be at the sole discretion of the treating physician. The overall study duration will be up to 42 months with an enrollment period of 18 months. Data will be collected by sites at Day 0 (baseline) and month 3 (M3), M6, M9, M12, M18, M24, M30, M36, and M42. Follow-up time for the first patient in will be up to 42 months and a minimum of 24 months for the last patient in. Patients will be followed until the end of study period, death, lost to follow-up, or study withdrawal, whichever comes first.

**Study Population:** Adult subjects diagnosed with early-stage EC/GEJC initiating nivolumab treatment per the clinical care recommendation of their treating physician and meeting the following inclusion criteria and none of the exclusion criteria will be eligible to participate in the study:

#### Inclusion criteria:

- 1. Patients aged 18 years or older at the time of informed consent
- 2. Patients provide voluntary informed consent to participate in the study before inclusion in the study
- 3. Confirmed diagnosis of resected early stage (Stage II/III) EC or GEJC (histologically or cytologically confirmed stage)
- 4. Physician decision to treat the patient with adjuvant nivolumab (according to the local label as per country-specific regulations) must be made prior to and independently of participation in the study

#### Exclusion criteria:

- 1. Participation in a clinical trial of an investigational drug, concurrently or within the last 30 days (patients who have completed their participation in an interventional trial and who are only followed-up for OS can be enrolled.)
- 2. Prior treatment with immuno-oncologic agents, including nivolumab, for any indication
- 3. Patients with a current primary diagnosis of a cancer other than EC or GEJC that requires systemic or other treatment, or has not been treated curatively (as per discretion of the investigator)

**Data Collection Methods:** Available data from patient's medical records will be entered into the electronic case report form (eCRF) by qualified site staff members. Patient-reported outcomes (PRO) used to assess satisfaction with nivolumab treatment will be completed on paper self-reported questionnaires by patients. Only data obtained according to routine clinical practice and addressing the study objectives will be collected and documented in the study.

**Data Analyses:** Evaluation of data will be primarily descriptive, and all collected data will be summarized overall and by subgroups of interests. Summary statistics for continuous variables will include the sample size (n), mean, standard deviation, median, minimum, and maximum. For categorical variables, numbers and percentages for each category will be provided and, for qualitative data, frequency and percentage per modality will be presented. The primary outcome will be DFS defined as the time from the date of nivolumab treatment initiation to the first date of disease recurrence or death, whichever occurs first. Time-to-event outcomes (i.e., DFS, OS) will be analyzed using the Kaplan-Meier methods and their corresponding 95% confidence intervals (CI) will be provided.

To address the objectives of the study, the following outcomes, but not limited to, will be assessed:

#### Primary outcomes

• Median DFS with 95% CI overall from nivolumab treatment initiation

#### Secondary outcomes

The following secondary outcomes will be assessed overall and by subgroups of interests depending on data availability, unless otherwise specified:

- Effectiveness outcomes in adult patients with early-stage EC or GEJC initiating adjuvant nivolumab treatment:
  - o DFS rates and median DFS with 95% CI in subgroup of interest
  - Median OS with 95% CI and OS rates
  - Median DMFS with 95% CI and DMFS rates
- Disease recurrence patterns
  - Median time to recurrence
  - Recurrence rates
  - Type of recurrence (local/regional vs. metastatic)
  - Median PRS with 95% CI and PRS rates
- Patient management and treatment patterns
  - Treatment history for EC/GEJC
  - o Nivolumab treatment duration, frequency, and dosing
  - Median with interquartile range (IQR) time between surgical resection and nivolumab initiation
  - Subsequent treatment(s) characteristics
  - Median TTNT with 95% CI
- Effectiveness outcomes in patients that receive subsequent treatment(s) following adjuvant nivolumab discontinuation:
  - Median OS with 95% CI and OS rates
  - Median PFS2 with 95% CI and PFS2 rates
  - o ORR
- Patient characteristics
  - Demographics and disease characteristics
  - Concomitant treatments
  - o Concurrent medical conditions
- Incidence and severity of AEs and SAEs related to nivolumab

#### Exploratory outcomes

• Treatment satisfaction prior to and after nivolumab treatment initiation and health related quality of life (HR-QoL) outcomes.

*Interim analysis:* There will be three interim analyses conducted in accordance with the scientific committee of the study.

**Sample Size/Power:** The sample size calculation is based on the primary outcome of the study and has been calculated assuming a 40% DFS rate after two years of follow-up and with an absolute precision of

7% for a sample size of 314 patients (accounting for a 10% drop-out rate). These calculations are based on assumptions from the CheckMate577 trial.

**Limitations/Strengths:** Although all possible measures will be taken to ensure quality and robustness of the data collected, there are some limitations that are inherent to the observational nature of this study including selection bias, attrition bias, and variability in local treatment practices, guidelines, and data quality across sites. Notably, selection bias due to non-consent will be mitigated by providing clear information to patients and physicians on the importance of the study and low burden of participation. Furthermore, the use of a large diverse sample of patients and prescribers from the US and Germany will contribute to the generalizability of the results. The site selection process will ensure that the sites participating are representative of the US and German landscape of EC or GEJC treatment.

Findings from this study will help support results from previous clinical trials and generate real-world effectiveness data in patients initiating nivolumab for the treatment of EC/GEJC. This study will provide a better understanding of the demographics, patterns of care, and clinical outcomes of patients with EC/GEJC treated with nivolumab in routine clinical practice and will be used to inform key stakeholders, patients, healthcare practitioners, guideline committees, and regulatory authorities.

## 1 INTRODUCTION

### 1.1 Study Rationale

Esophageal cancer (EC) is among the top 10 diagnosed malignancies worldwide, accounting for more than half a million new cases every year. It is the sixth leading cause of cancer mortality, with an estimated 500,000 deaths each year globally. The overall five-year survival of EC is less than 20%, with ranges from 5% to 47% depending on whether the cancer is localized, regional, or distant (metastatic). EC affects predominantly the elderly population, with the incidence of new cases peaking between 65 and 70 years of age. Men are disproportionally affected by EC, with a male to female ratio ranging from 3:1 to 4:1.

In the United States (US), it is estimated that in 2022, approximately 20,640 new cases (16,510 men and 4,130 women) of EC will be diagnosed, and 16,410 (13,250 men and 3,160 women) people will die from the disease, representing 3.4% of all cancer deaths in the country. In Germany, cancer registry data reported that in 2020, an estimated 7,900 new cases (6,100 men and 1,800 women) of EC were diagnosed and 6,500 people died from the disease, accounting for 2.6% of cancer-related mortality.

EC can be classified into two main histological subtypes: squamous cell carcinomas (SCC), which develop in epithelial mucosal cells located in the inner layer of the esophagus, most frequently in the cervical and upper and middle thoracic areas, and adenocarcinomas, which occur in glandular cells mainly located in the lower part of the esophagus. In the West, adenocarcinoma that arises from the gastroesophageal junction, which includes approximately the first two inches (5 cm) of the stomach (according to Siewert classification), is a rare type of cancer with epidemiological characteristics more similar to those of esophageal adenocarcinoma than gastric adenocarcinoma. Hence, in the US and European Union, gastroesophageal junction cancer (GEJC) is generally treated as other esophageal adenocarcinomas.

Worldwide esophageal SCC remains the most prevalent subtype, representing more than 85% of all incident cases of EC, especially in South America, Africa, and Asia. However, in Western countries, the incidences of esophageal adenocarcinoma and GEJC have been increasing dramatically over the past three decades and are predicted to surpass those of SCC in the upcoming years. Lifestyle risk factors for the development of esophageal SCC include low socioeconomic status, excess alcohol consumption, tobacco use, and micronutrient deficiencies. Esophageal adenocarcinoma and GEJC have been linked to obesity, tobacco use, gastroesophageal reflux disease, and Barrett's esophagus. A similar trend has been observed in Asia, possibly due to the current availability of Helicobacter pylori eradication therapy, a high prevalence of gastroesophageal reflux disease and obesity, and dietary factors.

Approximately 50% of ECs are locally or locoregionally advanced at presentation and thus amenable to potentially curative locoregional therapy. Neoadjuvant chemoradiotherapy followed by surgery is a widely used standard of care for patients with resectable, locally advanced esophageal adenocarcinoma or GEJC. However, only approximately 25% to 30% of patients treated according to the standard of care achieve a pathological complete response (pCR), resulting in a five-year survival rate of 50%. The remaining 70% to 75% of patients whose tumors do not achieve pCR (non-pCR) have a significantly lower five-year survival rate of 37%, and this is even lower in lymph node-positive patients, where the five-year survival is

17%. This highlighted the need for adjuvant treatments to improve survival and health outcomes in these patients.

In recent years, immune checkpoint inhibitors, especially those that target the programmed cell death protein-1 (PD-1) / programmed cell death ligand-1 (PD-L1) axis have been the subject of increased interest as clinical data have demonstrated their efficacy against various malignancies, including EC. PD-1 and PD-L1 inhibitors have also presented a broad anti-cancer therapeutic use, including as diagnostic tool and neoadjuvant and adjuvant therapies.

Nivolumab (Opdivo®; Bristol Myers Squibb [BMS]) is a fully human immunoglobulin G4 monoclonal antibody that binds to the PD-1 receptor, and which is used in patients with EC/GEJC as adjuvant therapy. PD-1 is an inhibitory receptor expressed on activated T cells that can negatively regulate T cell-mediated immune responses and promotes tumor development; by interacting with PD-1, nivolumab blocks PD-1 interaction with the ligands PD-L1 and PD-L2. This enables the release of PD-1 pathway-mediated inhibition of T cell immune response, including the anti-tumor immune response, thereby reducing tumor growth, and promoting tumor rejection.

The efficacy and safety of nivolumab in patients with resectable, locally advanced EC or GEJC has been demonstrated in CheckMate 577 (NCT02743494), a global, randomized, double-blind, placebo-controlled phase III trial that evaluated nivolumab as adjuvant treatment after neoadjuvant chemoradiotherapy and surgery. The trial population consisted of adult patients with resected (R0) stage II or III EC or GEJC who had received neoadjuvant chemoradiotherapy and had residual pathological disease. A total of 794 patients were randomly assigned at a ratio of 2:1 to receive nivolumab (532 patients) or placebo (262 patients, including two patients who did not receive the placebo). Patients were administered nivolumab at a dose of 240 mg every two weeks for 16 weeks, followed by nivolumab at a dose of 480 mg every four weeks or matching placebo. The trial intervention lasted for a maximum duration of a year. The primary efficacy endpoint was disease-free survival (DFS), defined as the time between randomization and the first recurrence (local, regional, or distant from the primary resected site) or death, from any causes, as assessed by the investigator prior to subsequent anti-cancer therapy. The median follow-up duration was 24.4 months at primary completion interim analysis.

Among patients who received nivolumab, the median DFS was doubled as compared with patients who received placebo: 22.4 months (95% confidence interval [CI] 16.6 to 34.0) vs. 11.0 months (95% CI 8.3 to 14.3). The hazard ratio for disease recurrence or death was 0.69 (96.4% CI 0.56 to 0.86; p<0.001). The efficacy of nivolumab compared with placebo was observed across multiple prespecified subgroups based on demographic and baseline disease characteristics, including age group ( $\geq$ 65 and <65), sex, race, region, disease stage at diagnosis (II and III), histologic type (SCC and adenocarcinoma), and tumor cell PD-L1 expression. More than half of the trial patients had lymph node-positive disease at baseline and, despite the poor prognosis in these patients, nivolumab was associated with improvement in DFS, with a 31% reduction in the risk of recurrence or death.

The safety profile of nivolumab was consistent with those observed in previous trials in patients with gastroesophageal and other solid tumors. Grade 3 or 4 adverse events (AE) that were considered by the investigators to be related to the trial regimen were more common in the nivolumab group (in 71 of 532 patients [13%]) compared with the placebo group (in 15 of 260

patients [6%]). The most common grades 3 or 4 select treatment-related AEs (TRAEs) in the nivolumab group were pneumonitis (in four patients [<1%]) and rash (in four patients [<1%]). In the placebo group, each of these AEs was observed in one patient each (<1%). The most common AEs of any grades that were classified as related to the trial regimen by the investigators were fatigue, diarrhea, pruritus, and rash in the nivolumab group and diarrhea and fatigue in the placebo group.

Based on the results of CheckMate 577 trial, in May 2021 and July 2021, the Food and Drug Administration (FDA) and European Commission, respectively, approved nivolumab for patients with resected EC or GEJC with residual pathologic disease who have received neoadjuvant chemoradiotherapy.

To improve the understanding of the effectiveness and health benefits of nivolumab treatment beyond the randomized controlled trials (RCT) setting, the present prospective, multicountry, multicenter, observational study has been designed to collect real-world data during the postmarket authorization approval period. This study aims to describe the real-world effectiveness, patient characteristics, treatment patterns, AEs, and patient satisfaction with nivolumab in patients with early stage (II or III) EC or GEJC initiating treatment in routine clinical practice in the US and Germany.

## 1.2 Research Questions

This study aims to address the following research questions:

- What is the real-world effectiveness of adjuvant nivolumab overall and according to various subgroups of interest?
- What is the profile of patients initiating adjuvant nivolumab?
- What is the pattern of use of adjuvant nivolumab, including dosing, regimen, indication, treatment rationale, treatment duration, modifications in relation to the management of AEs, and reasons for treatment discontinuation?
- What are the subsequent treatments and the outcomes in patients that receive these treatment(s) following adjuvant nivolumab?
- What is the patient HR-QoL and satisfaction with adjuvant nivolumab treatment?

# 2 OBJECTIVES

# 2.1 Primary Objective

The primary objective of this study is to estimate real-world disease-free survival (DFS) in adult patients with early-stage esophageal cancer (EC) or gastroesophageal junction cancer (GEJC) initiating adjuvant nivolumab treatment.

### 2.2 Secondary Objectives

The following secondary objectives will be assessed overall and according to various subgroups of interest, unless otherwise specified:

- To estimate in adult patients with early-stage EC or GEJC initiating adjuvant nivolumab treatment:
  - DFS and DFS rates in subgroups of interest only
  - $\circ$   $\,$  Median overall survival (OS) and OS rates  $\,$
  - Distant metastasis-free survival (DMFS) and DMFS rates
- To describe treatment patterns of adjuvant nivolumab (dosing, regimen, indication, treatment rationale, treatment duration, modifications in relation to the management of AE, reasons for treatment discontinuation/cessation) and subsequent therapy (regimen, duration) and time to next treatment (TTNT)
- To estimate from initiation of subsequent treatment, in patients that receive subsequent treatment(s) following adjuvant nivolumab discontinuation:
  - OS and OS rates
  - Progression free survival 2 (PFS2) and PFS2 rates
  - Overall response rate (ORR)
- To describe disease recurrence patterns in patients with a recurrence, including time to recurrence, type of recurrence (local/regional vs metastatic), and PRS
- To describe sociodemographic and clinical characteristics, and treatment history
- To describe incidence and severity of AEs and SAEs in relation to nivolumab

## 2.3 Exploratory Objective

The exploratory objective of this study is to evaluate patient satisfaction with adjuvant nivolumab treatment using the Cancer Therapy Satisfaction Questionnaire (CTSQ) and HR-QoL by using the Functional Assessment of Cancer Therapy – General 7 (FACT-G7) questionnaire.

## 3 STUDY DESIGN

### 3.1 Overview of Study Design

This is a non-interventional, prospective, multinational, multicenter, post-marketing observational study designed to describe the real-world effectiveness and patterns of use of adjuvant nivolumab in patients with early stage (Stage II/III) EC or GEJC. This study will be conducted in the US and Germany will collect data available from patients' medical files and other items routinely collected during disease management in clinical practice and patient-reported outcomes (PRO) related to treatment satisfaction and quality of life.

This study is strictly observational and does not result in interference with standard medical care; thus, it will not impact the treatment of study participants. Prescriptions of nivolumab will be at

the sole discretion of the treating physician. Patients are to be enrolled into this noninterventional, primary data collection study no earlier than the decision to initiate treatment with nivolumab and no later than the first dose of nivolumab treatment. It is mandatory that the treating physician's decision to start treatment with nivolumab for early-stage EC or GECJ is taken independently and before the decision to invite the patient to participate in the study. Day 0 corresponds to the day of nivolumab initiation (administration of the first dose of treatment). The local investigator is responsible for the exact procedures of administration of nivolumab, and concomitant medications and therapies deemed necessary for the supportive care and safety of the patients.

Once the decision to prescribe nivolumab is taken by the medical team/physicians according to usual practice, patients will be screened for selection criteria. If the patient meets all inclusion criteria and none of the exclusion criteria, the investigator should then invite the patient to participate in the study and collect their consent to participate. Enrollment in the study is then clearly distinguished from the therapeutic decision to initiate nivolumab.

Physicians will be asked to enroll eligible patients consecutively until the total expected study sample size is reached or the end of the enrollment period (whichever occurs first). The enrollment period is anticipated to last approximately 18 months. The follow-up time will vary between patients due to the nature of the study with ongoing enrollment; patients will be followed for up to 42 months for the first patient in and up to 24 months for the last patient in. Patients will be followed until the end of study period, death, lost to follow-up, or withdrawal, whichever comes first. Patients will be censored at last record or assessment for those lost to follow-up.

Assessment schedules will be performed according to routine local clinical practice. Data collection and data entry by sites will start at Day 0 (baseline, i.e., the day of nivolumab initiation), and at the following months with a time window of +/- 15 days: months 3, 6, 9, 12, 18, 24, 30, 36, and 42 counted relative to treatment initiation (two and 3.5 years after nivolumab initiation for the first and last patient in, respectively). As this is a non-interventional study, no visits or measurements will be made mandatory by the protocol, and data collection at these prespecified timepoints will only take place if the patient visits the site as per standard of care. Investigators or qualified research staff should collect data from the visit nearest to the time point.

Sites will receive fees to compensate for the time spent for data collection and entry into eCRFs. Since the study is intended to reflect usual clinical practice, physicians will not be required to perform any mandatory patient assessments or laboratory tests that they would not ordinarily do in treating their patients. This protocol requires that sites submit all relevant documentation to their respective institutional review board (IRB) or Ethics Committee (EC) and obtain approval or acknowledgment of notification, depending on the local requirements. Participating patients must provide written informed consent prior to study commencement, and they have the right to withdraw from the study at any time. This study will be conducted with support of a clinical research organization (CRO).

An overview of study design and data collection is shown in Figure 1.

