DFS	Time-to-event	Time between initiation of nivolumab treatment and the first date of recurrence (local, regional, or distant from the primary resected site) or death from any causes, whichever occurs first, as assessed by the investigator prior to subsequent anti-cancer therapy.
DFS rates	Continuous	DFS rates are defined as the probability that a patient is alive and presents no signs of recurrence at specific time points, following adjuvant nivolumab initiation.
08	Time-to-event	Time between initiation of nivolumab treatment until date of death due to any cause. Patients who are alive at last visit will be censored on date last known to be alive.
OS rates	Continuous	OS rates are defined as the probability that a patient is alive at specific time points, following adjuvant nivolumab initiation.
DMFS	Time-to-event	Time between initiation of nivolumab treatment and date of appearance of distant metastasis or death from any causes, whichever occurs first, as assessed by the investigator prior to subsequent anti-cancer therapy.
DMFS rates	Continuous	DFS rates are defined as the probability that a patient is alive and presents no signs of metastasis at specific time points, following adjuvant nivolumab initiation.
Time to recurrence	Continuous	Time between initiation of nivolumab treatment and the first date of recurrence.
Recurrence rates	Categorical	Recurrence rates are defined as disease recurrence (i.e., local/regional, metastatic) at specific time points, following adjuvant nivolumab initiation.
PRS	Time-to-event	PRS is defined as the interval from the date of any recurrence to the date of death from any cause. Patients who are alive at last visit will be censored on date last known to be alive.
Effectiveness outcomes in pati discontinuation:	ients that receive s	ubsequent treatment(s) following adjuvant nivolumab
OS of subsequent treatment	Time-to-event	Time between initiation of subsequent treatment until date of death due to any cause. Patients who are alive at last visit will be censored on date last known to be alive.
OS rates of subsequent treatment	Continuous	OS rates are defined as the probability that a patient is alive at specific time points, following subsequent treatment initiation.

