Recurrence	
 
Yes/No
 
Date of recurrence
 
Type of recurrence (i.e., local, regional, distant)
 
	
Disease progression	
 
Yes/No (as assessed by investigator or RECIST criteria)
 
Date of disease progression
 
	
Medical imaging test to assess treatment outcomesMedical imaging test used to assess recurrence of progression (e.g., computed tomography (CT) / r resonance imaging (MRI), Conventional X-ray, I details including method of assessment (i.e., by I or as assessed by the treating physician) and date assessment		All visits 
Death	

Yes/No

Date of death

Cause of death

	

 Data will be collected at visits Day 0, and Months 3, 6, 9, 12, 18, 24, 30, 36, and 42.

Abbreviations: AEs = adverse events; CT = computed tomography; EC = esophageal cancer; GEJC = gastroesophageal junction cancer; MRI = magnetic resonance imaging; PET = positron emission tomography; RECIST= Response evaluation criteria in solid tumors; TNM=Tumor Node Metastasis

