#### Attrition bias

In a prospective observational study, patients who are lost to follow-up or withdrawn from the study are the main source of attrition bias This bias may compromise sample representativeness and impact the interpretation of the results if there are significant differences in baseline characteristics or outcomes between patients that remain in the study and those who are lost to follow-up. If the proportion of patients lost to follow-up is non-negligible, the target precision for the primary outcome may not be reached and impact the interpretation of the findings.

To prevent this risk and minimize its potential impact, all efforts will be made to collect data from the closest previous visit and physicians will be encouraged to contact the patient to receive survival information and the vital status of patients lost to follow-up or who withdrawn from the study. A discontinuation case report form will be provided to physicians to document the reasons for discontinuation in the study.

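### Follow-up data are collected only when the patient attends, and no step retrieves recurrence for patients who stop attending, so DFS and DMFS risk being biased upward.

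*Protocol*

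**What the plan says.** Protocol section 3.1 sets data entry at Day 0 and at "months 3, 6, 9, 12, 18, 24, 30, 36, and 42 counted relative to treatment initiation", each with a window of 15 days either side. It states that "no visits or measurements will be made mandatory by the protocol" and that "data collection at these prespecified timepoints will only take place if the patient visits the site as per standard of care". The next sentence says that "Investigators or qualified research staff should collect data from the visit nearest to the time point". On loss, the same section says: "Patients will be censored at last record or assessment for those lost to follow-up".

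Table 3 (section 3.5.1.2) lists recurrence with its date and type, and death with its date and cause, as items for all visits. Its footnote reads: "Data will be collected at visits Day 0, and Months 3, 6, 9, 12, 18, 24, 30, 36, and 42".

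Table 2 (section 3.5.1.1) defines DFS by first recurrence or death, and DMFS by distant metastasis or death. For OS it says: "Patients who are alive at last visit will be censored on date last known to be alive".

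Section 5.1, under attrition bias, says that "physicians will be encouraged to contact the patient to receive survival information and the vital status of patients lost to follow-up", and extends this to patients who withdraw. It also asks sites to use data from the closest earlier visit and provides a discontinuation form.

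**The concern.** The study reads medical files, and a site can read a file without the patient being present. Waiving mandatory visits is enough to keep the study non-interventional. The further condition that the patient must attend is not needed for that purpose, and it ties data collection to something that may depend on the outcome.

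A patient who is well keeps routine appointments and is recorded. A patient who relapses and moves to another centre or to palliative care may stop attending. Under section 3.1 that patient is censored at an earlier, event-free date. Kaplan-Meier estimation assumes that censored patients have the same later risk as those still followed. If relapse is the reason for leaving, that assumption fails and the curve sits too high. A larger sample does not remove this.

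The primary outcome is exposed, and so is DMFS. The protocol says that the findings should help support earlier trial results, and section 1.1 quotes a median DFS of 22.4 months from the pivotal trial. An upward bias could make real-world results look closer to that figure than they are.

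**Working it through.** **1. Which events have a retrieval route once the patient stops attending**

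- Death: encouraged contact (section 5.1); an instruction at withdrawal to try to document outcome (section 6.1.2); SAE reporting of deaths known to the site (section 7).
- Recurrence or metastasis, with date and type: section 6.1.2 could cover it at withdrawal, but names neither. For a patient who simply stops attending, no section requires it. The closest-earlier-visit measure in section 5.1 looks back to a time before the missed event.

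The gap is therefore in DFS and DMFS rather than in OS.

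**2. Inputs from the plan (section 4.2)**

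Two-year DFS 40%, absolute precision 7 points, N = 285, or 314 with 10% drop-out. The usual single-proportion formula does not return 285: 1.96² × 0.4 × 0.6 / 0.07² gives 189. That is a separate matter. Here it matters only that 285 evaluable patients give a half-width of 1.96 × √(0.24/285) = 5.7 points, so two yardsticks are available: the stated 7 points and 5.7 points.

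**3. Size of the bias (assumptions)**

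Assume exponential DFS with S(24) = 0.40. Then λ = −ln(0.4)/24 = 0.0382 per month and the median is ln 2/λ = 18.2 months. Let q be the share of events never entered. If those patients are censored at the event time:

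- apparent S(24) = 0.4^(1−q)
- apparent median = 18.2/(1−q)

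A simulation of 400,000 patients used the protocol's visit times and 24 to 42 months of follow-up, and censored each missed event at the last scheduled visit before it.

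The documents give no q, but the planned drop-out gives a reference case. With DFS of 40%, 60% of patients have an event by month 24. If all of the 10% drop-outs hide such an event, q = 10/60 = 16.7%.

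| q | Closed form S(24) | Simulated S(24) | Bias, points | Median, months (closed form / simulated) |
|---|---|---|---|---|
| 0 | 40.0% | 40.0% | 0 | 18.2 / 18.1 |
| 5% | 41.9% | 41.7% | 1.7–1.9 | 19.1 / 19.0 |
| 10% | 43.8% | 43.5% | 3.5–3.8 | 20.2 / 20.0 |
| 16.7% | 46.6% | about 46.1% (interpolated between 45.4% at 15% and 47.4% at 20%) | 6.1–6.6 | 21.8 / about 21.4 (interpolated) |

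**4. Two checks on the mechanism**

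- Loss of 10% of patients unrelated to outcome: simulated S(24) = 40.0%. No bias.
- Every death retrieved and only recurrences missed. Further assumptions: 80% of first events are recurrences and median survival after recurrence is 6 to 18 months. Missing 10% of recurrences (8% of all first events) gives 41.3 to 42.9%. Missing 20% (16% of all first events) gives 42.6 to 45.8%. OS is unbiased. The DFS bias shrinks but does not vanish, because the event is counted at death and not at the earlier recurrence.

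**The case against.** The protocol has more safeguards than section 3.1 alone suggests, and several stronger readings should be set aside.

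- A reader might infer that encouraged contact is the only back-up. It is not. Section 6.1.2 asks for outcome to be documented at withdrawal. Section 7 treats death as an SAE: non-related events are reportable until 100 days after the last dose and related events without limit. For a patient completing 12 months of treatment, 100 days takes this to about month 15. Table 2 censors OS when the patient was last known alive, not at the last attended visit. The OS concern is therefore weak.
- A reader might infer that an event between visits is lost. It is not lost for that reason alone: if the patient returns or the record reaches the site, it can be entered with its actual date.
- After month 12 the windows cover about 30 of every 183 days (16%). That is not a loss rate. The window locates data entry, and the nearest-visit sentence admits off-schedule visits, although the two rules do not sit well together.
- One might take 20% of events as missed, which gives 47.4 to 48.0% and a bias above 7 points. By month 24 that is 0.20 × 60% = 12% of all patients, more than the plan's whole drop-out allowance.
- Attrition bias is acknowledged, missing-data sensitivity analyses are promised, and detailed censoring rules are left to an SAP that is not shown.

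All of this stands, and it narrows the point. It does not close the gap for DFS and DMFS. The nearest-visit rule still presupposes a visit, the withdrawal instruction does not address silent non-attendance, and a sensitivity analysis can vary assumptions about uncollected recurrences but cannot recover them. The attendance condition is fixed in the protocol.

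**Conclusion.** The point holds as a risk. The attendance condition, censoring at last record, and the absence of any required retrieval of recurrence or metastasis status together leave DFS and DMFS open to informative censoring. The bias is upward if relapse is what stops attendance.

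The documents do not establish that estimates will be inflated, because they give neither a share of missed events nor the reasons for non-attendance. On the assumptions shown, 24-month DFS would read about 42 to 44% instead of 40% with 5 to 10% of events missed. It would read 46 to 47% in the reference case where every planned drop-out hides an event. That last bias stays just under the stated 7 points and slightly above the 5.7-point half-width that 285 patients would give. It is smaller if all deaths are retrieved. OS is affected only where vital status stays unknown.

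**What to change.** In section 3.1, keep the statement that "no visits or measurements will be made mandatory by the protocol" and replace the attendance condition with wording such as:

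*At each timepoint the site completes the eCRF from the available medical record, including outside reports and death notices, whether or not the patient attended. It enters any recurrence (date and type), subsequent anti-cancer therapy and vital status since the previous entry, within the consent limits of section 6.1.2.*

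Align the Table 3 footnote with this. Apply the 15-day window only to questionnaires and point measurements such as weight and ECOG, which also resolves the tension with the nearest-visit sentence. Report completeness of follow-up alongside DFS and DMFS.

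The cost is protocol and eCRF-guideline wording plus a short chart check for non-attenders. No visit or procedure is added, sites are already paid for data entry, and patients who withdraw consent to further data use remain excluded.
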